1. *Ambulatory Stress Assessments*, delivered to participants' smartphones at T1, T3, and T5, will assess (1) EMA stress (state stress perceptions, stress events) and resilience (state positive/negative affect, social interactions) four times daily during between 8am and 8pm, and (2) average daily life stress via diary (stress perceptions, stress events), resilience (positive/negative emotions, social interactions), and intervention practice (T3, T5 only). At T2, participants will complete stress surveys before and after each intervention lesson, before and after each JIT prompt, and each evening, which will inform adherence and JIT prompt timing.
2. *Ambulatory Physiology*, tracked and stored via Fitbit wearable device throughout T1-T5, will include continuous HR data (via photoplethysmography) to pair with EMA stress surveys. Physiological data and continuous physical activity (via pedometer) and sleep (via actigraphy) data will be integrated daily into the AWARE database and will be used in machine learning analyses with passive sensor data to evaluate predictive models of state stress in daily life.
3. *Smartphone Passive Sensor Data* will be collected throughout T1-T5. The open-source AWARE application will be installed on participants' Android or iOS smartphones to continuously and unobtrusively collect data characterizing behavioral and contextual features. Sensor data will include device usage, location, movement, activity, noise, conversation, and communication; these features will be used to predict stress.
4. *Inflammatory biomarkers* will be quantified in batch from DBS samples collected at T1, T3, and T5. Pro-inflammatory cytokine IL-6 will be assessed using R&D's Ella Automated Immunoassay System. A larger panel of pro- and anti-inflammatory markers (e.g., TNF, CRP, IL-8, IL-10) will be assessed via multiplex with additional funding.

Eligibility Criteria:

Inclusion Criteria:

1. Emerging adults between 18 and 29 years old
2. English speaking
3. History of adverse childhood experiences (specifically, moderate-to-severe physical, emotional, or sexual abuse in childhood: scoring >9, >12, or >7 on respective

Childhood Trauma Questionnaire subscales 1)

4. Data-enabled Android or iOS smartphone
5. Able to meet study requirements

Exclusion Criteria:

1. Self-reported diagnosis of chronic physical disease (e.g., cancer, HIV, heart disease, diabetes, bleeding disorder)

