2. Self-reported diagnosis of chronic mental disorder (e.g., schizophrenia, personality disorder, or psychotic illness) major neurological disorder, or suicidal thoughts or wishes at baseline
3. Medication use that interferes with HPA-axis activity (e.g., corticosteroids) or autonomic activity (e.g., antihypertensive medication)
4. Current antibiotic, antiviral, or antimicrobial treatment
5. Shift workers
6. Pregnancy or breastfeeding
7. Excessive alcohol use
8. Frequent illicit drug use
9. Regular systematic mind-body practice (>2 times per week)

Statistical Analysis Plan (SAP)

Power:

Sample size balances rules of thumb for pilot trial sample size (which range from 25-35 participants per treatment arm estimating a small between-group effect size, with larger pilot trials more accurately estimating variance and allowing for smaller sample sizes in efficacy trials) with calculations to detect medium within-group effects of mindfulness on EMA stress ($d=.40$). Therefore, we plan to enroll 80 participants (40 per condition).

Statistical Analysis Plan:

This study will evaluate two primary aims and one exploratory aim:

Aim 1 evaluates the feasibility and acceptability of the interventions and assessments, with the prediction that interventions and assessments will meet feasibility and acceptability benchmarks in this ELA sample, and mindfulness and control groups will show equivalence on these measures.

- Planned analysis: Feasibility and acceptability will be evaluated by comparing screening and enrollment numbers, participant retention, adherence to intervention and assessment protocols, treatment expectancies, intervention fatigue, and prompt timing to proposed benchmarks for success. Specifically, minimum feasibility benchmark ranges are as follows: 10% of those screened will be eligible; 60-70% of eligible participants will enroll; <10% of participants will show increases in daily stress, a measure of safe implementation; 80-90% of enrolled participants will be retained through the intervention period and 75-85% through the follow-up assessment period; participants will complete 85-95% of the intervention lessons, 60-70% of practice prompts, 75-90% of ambulatory assessments, and provide mobile sensor data on >75% of days. ANOVAs will test for equivalence of mindfulness vs. control groups on

feasibility and acceptability outcomes.

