Aim 2 tests for mindfulness intervention changes to establish effect sizes for a future RCT, with the prediction that mindfulness training will reduce daily life stress, normalize stress biology, and reduce markers of inflammation from pre-intervention to post-intervention and one-month follow-up.

- Planned analysis: MLMs will be used to test for mindfulness intervention changes in daily life subjective stress events and perceptions, stress-related HR in daily life (HR during high stress surveys relative to average person-centered HR), and markers of inflammation from pre-intervention to post-intervention and one-month follow-up. Secondary MLM analyses will test for mindfulness intervention changes in daily life resilience (positive/negative affect; social factors) and daily life HRV. Tertiary MLM analyses will test for between-group differences (mindfulness vs. coping intervention) on all outcomes.

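### The safe-implementation benchmark (<10% of participants with increased daily stress) sets no minimum increase, and the cut-off chosen largely decides whether it is met

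*Combined protocol and SAP*

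**What the plan says.** The SAP's Aim 1 planned analysis lists numeric benchmarks for success. The one for safety reads "<10% of participants will show increases in daily stress, a measure of safe implementation". The Study Objectives place safe implementation within the first primary hypothesis, and this is the only numeric criterion given for it. The same paragraph adds that "ANOVAs will test for equivalence of mindfulness vs. control groups on" the feasibility and acceptability outcomes, so a comparison by arm is already intended.

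The sentence gives no minimum increase, instrument, comparison period or denominator. Under Measures, the ambulatory assessments cover "EMA stress (state stress perceptions, stress events" as well as "average daily life stress via diary (stress perceptions, stress events". There are also evening and pre/post surveys during the intervention, and the Perceived Stress Scale at each visit. Aim 2, by contrast, names its constructs ("test for mindfulness intervention changes in daily life subjective stress events and perceptions") and its period ("markers of inflammation from pre-intervention to post-intervention and one-month follow-up").

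**The concern.** A limit on the proportion of people who get worse has meaning only once getting worse is defined. Without a minimum increase, the default reading is that any positive difference counts. A weekly stress score varies from week to week in everyone, so under no effect it is about as likely to go up as down. A 10% limit is then far below what chance alone produces.

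Two things are at stake. Applied as any rise, the benchmark would report a safety failure for a harmless intervention. If the cut-off is settled after the data are seen, the same data can be made to pass or fail. Either outcome would misinform the efficacy trial that this pilot is meant to prepare.

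**Working it through.** The plan gives no probability of meeting this benchmark, so there is no figure of its own to reproduce.

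**Inputs from the document.** Limit: fewer than 10% (Aim 1). Enrolment: 80, 40 per arm (Power). Effect: d=.40, from "calculations to detect medium within-group effects of mindfulness on EMA stress" (Power). Retention: "80-90% of enrolled participants will be retained through the intervention period and 75-85% through the follow-up assessment period". That gives 80 × 0.80 = 64 to 80 × 0.90 = 72 scorable after the intervention, and 80 × 0.75 = 60 to 80 × 0.85 = 68 at follow-up.

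**Assumed, because the document gives no values.** Normally distributed change scores; pre-post correlation r from 0 to .95; 10-30% ties where ties are considered.

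**The limit as a count.** At most 5 of 60, 6 of 64, 6 of 68, 7 of 72, 7 of 80, or 3 of 40.

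**Any rise, no true change.** The share rising is p = 1 − Φ(0) = 0.50. The exact binomial chance of passing is P(X ≤ 6 | 64, 0.5) = 4.5e-12. It is 2.9e-15 at n=80 and 9.7e-9 in one arm of 40. Ties lower p to 0.5 × (1 − 0.10) = 0.45 or 0.5 × (1 − 0.30) = 0.35, and the chance at n=64 is then 6e-10 or 2.4e-6. If a rise at either T3 or T5 counts, with equal week variances (correlation .5 between the two changes), the share rising is 1 − (1/4 + asin(.5)/2π) = 0.67.

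**Any rise, with the planned benefit.** With d on the baseline SD, dz = .40/√(2(1 − r)) and p = 1 − Φ(dz). If only the mindfulness arm benefits, the overall share is the average of p and 0.5. Chances are ranges over n = 60 to 72.

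| r | Share rising, benefit in both arms | Chance of passing | Share rising, mindfulness only | Chance of passing |
|---|---|---|---|---|
| 0 | 0.389 | <0.001 | 0.444 | <0.0001 |
| .5 | 0.345 | <0.001 | 0.422 | <0.0001 |
| .8 | 0.264 | 0.0003-0.0007 | 0.382 | <0.0001 |
| .9 | 0.186 | 2-3.5% | 0.343 | at most 1.4e-6 |
| .95 | 0.103 | 41-53% | 0.301 | at most 1.7e-5 |

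**Effect of the cut-off, no true change.** With a cut-off of c SDs of the change score, p = 1 − Φ(c).

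| c | Share flagged | Pass, n=64 | Pass, n=80 | Pass, n=40 |
|---|---|---|---|---|
| 0 | 0.500 | 4.5e-12 | 2.9e-15 | 9.7e-9 |
| 0.5 | 0.309 | 0.004% | <0.001% | 0.04% |
| 1 | 0.159 | 10% | 5% | 10% |
| 1.5 | 0.067 | 87% | 84% | 72% |
| 1.96 | 0.025 | 99.9% | 99.9% | 98% |

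At n=64 the benchmark becomes more likely to pass than fail at about 1.26 SD of change.

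**The case against.** **The authors surely meant a meaningful increase.** Probably so, and the document nowhere says that any rise counts. A reader might infer from the near-zero figures that the plan commits itself to an impossible rule. It does not: those figures show what the sentence does if applied literally. But cut-offs of 1 and 1.5 SD of change could each be called meaningful, and they give 10% and 87%. The intended value has to be written down.

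**The document has a cut-off that could be borrowed.** The exploratory section defines high-stress prompt times as at least 1 SD above the person's own mean. Nothing links that to the safety benchmark, and borrowing it settles little. On a seven-day diary mean with no change, the flagged share is 1 − Φ(1/√((2/7)(1 + w))), where w is the week-to-week variance relative to the sampling variance of the weekly mean. At n=64 the pass chance is 99.7% at w=0, 62% at w=1, 19% at w=2 and 5% at w=3. The document gives no w.

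**Instrument and period are nearly readable.** This largely stands. The diary and the changes from T1 to T3 and T5 are the nearest readings, so these are secondary gaps. The benchmark still does not state them.

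**Any rise is not always hopeless.** Correct. If both arms improved by d=.40 and r were near .95, it would pass about half the time. The sample-size text posits that effect for mindfulness only.

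**It is a pilot, and safety is followed elsewhere.** Staff check-ins on intervention days 3, 9 and 14, the Adverse Effects Survey and symptom scales stand apart from this benchmark. That limits the consequence, but none of them carries a pass limit or repairs this one.

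**Conclusion.** The point holds and should be fixed. The benchmark belongs to a primary hypothesis, yet it lacks the one quantity that determines its result. With no true change and n=64, the chance of meeting it runs from about 5e-12 (any rise) to 99.9% (1.96 SD of change). Literal use would almost certainly report failure, except where both arms improve and scores are very highly correlated.

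The absence of a minimum increase is certain from the text. The probabilities rest on normal change scores and on assumed values of r, ties and w. The conclusion that the cut-off decides the result is the same at n=40, 64 and 80.

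A reader might go further and infer that participants are left unprotected. The document does not support that: it ties no stopping rule to this figure, and adverse events are monitored separately. The harm is a feasibility and safety statement that could mislead in either direction.

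**What to change.** Before T3 or T5 outcomes are examined, state in the SAP:

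1. **Measure:** one, for example the weekly mean of diary stress perception.
2. **Comparison:** T1 to T3 as primary, with T1 to T5 reported separately.
3. **Minimum increase:** a number in scale points that uses no post-baseline data, for example 1.96 × √(2 × (s²/7) × (1 + w)). Here s² is the pooled within-person day-to-day variance at T1 and w is a pre-stated allowance for week-to-week variance. In units of s this is 1.05 at w=0, 1.28 at w=0.5, 1.48 at w=1 and 1.81 at w=2. Show results over a range of w. The 7 assumes complete diaries; at the plan's 75% completion it becomes 5.25, which alone multiplies s²/7 by 1.33.
4. **Denominator:** participants with T3 data, with the number missing shown beside it.

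Report the proportion overall and by arm with exact 95% CIs.

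Do not take the cut-off from a residual SE over all three weeks. It needs T3 and T5 outcomes, and true worsening inflates it. With 32 per arm and 6 in each arm truly rising by 2 SEs, the limit was breached in 17% of simulated trials under that rule, against 68% with a cut-off truly fixed at 1.96 SEs.

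The cost is a few SAP sentences and no added data, since the diary is already scheduled at T1, T3 and T5. There are downsides. The allowance w is an assumption: if w=0 is stated and the truth is 2, then 1 − Φ(1.96/√3) = 13% are flagged with no change. Small true rises are not counted, and people who leave because of distress are not scored. Precision is low: 6 of 64 passes with a 95% CI of 4-19%, and 3 of 32 in one arm has 2-25%.

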T2: Two-week intervention. Following baseline assessments, participants will be randomly assigned to the mindfulness intervention or coping control intervention condition. Participants will complete one 20-minute audio-guided lesson each day, plus receive 3 brief text-based practice prompts daily at random times. The interventions were developed by [name] and [name] and are matched on attentional demand, lesson length and structure, and voice. Interventions will be delivered via smartphone app that securely tracks participant activity, including timestamps at lesson and practice prompt start/completion and daily survey responses (stress assessments pre- and post-lesson, pre- and post-practice prompt, and each evening; practice prompt receptivity). This data will be integrated with phone sensor and wearable data to inform future JIT intervention tailoring. Staff will check in with participants on intervention days 3, 9, and 14 to provide support and monitor for adverse events.

Mindfulness intervention: Based on [name]'s Unified Mindfulness system, lessons train meditation techniques for 3 mindfulness skills: (1) concentration, a stable attention on present-moment body experiences; (2) sensory clarity, the detection and discrimination of sensory experiences; and (3) equanimity, an attitude of acceptance and receptivity toward present-moment experiences. Practice prompts build on the skills trained in each lesson, encouraging participants to practice brief moments of mindful awareness, mindfulness while doing daily tasks, or formal meditation for 5-10 minutes.

Coping control intervention: To parallel the structure of the mindfulness intervention without training present-moment attention or acceptance skills, participants are instructed to: (1) reflect and mind wander; (2) reappraise past and future events; and (3) analyze and solve personal problems. Practice prompts encourage participants to take brief mind-wandering breaks, apply reappraisal or problem-solving skills, or reflect for 5-10 minutes. This program controls for nonspecific effects (e.g., goals, daily practice, and treatment expectancies). Here, an active control program will inform the feasibility of the RCT design for future trials and will preempt differential dropout issues that are commonly seen in studies using no-treatment control groups.

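### Aim 1 predicts that the arms are equivalent on feasibility and acceptability, but the planned ANOVAs, with no margin, can only test for a difference

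*Combined protocol and SAP*

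**What the plan says.** The Aim 1 prediction in the Statistical Analysis Plan has two parts. The first is that the interventions and assessments will meet the feasibility benchmarks. The second concerns the arms: "mindfulness and control groups will show equivalence on these measures".

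The planned analysis compares observed figures with numeric benchmarks, for example "80-90% of enrolled participants will be retained through the intervention period". It then closes with the between-arm analysis: "ANOVAs will test for equivalence of mindfulness vs. control groups on" the feasibility and acceptability outcomes.

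No equivalence margin, two one-sided tests procedure, confidence-interval rule or alpha appears anywhere in the document. The Power section ("we plan to enroll 80 participants (40 per condition") rests on pilot rules of thumb and "calculations to detect medium within-group effects of mindfulness on EMA stress" with d = 0.40. Neither basis concerns equivalence between arms.

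In Procedures, under the coping control intervention, the active control is justified partly because it will inform the feasibility of the RCT design and "will preempt differential dropout issues that are commonly seen in studies using no-treatment control groups".

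**The concern.** The hypothesis and the test point in opposite directions. To support equivalence, the data must rule out differences larger than a stated amount. ANOVA asks whether the data rule out a difference of zero. A non-significant F can mean that the arms are alike or that the sample is too small to tell, and the smaller the sample, the more easily it arises.

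The plan gives no decision rule. The evident reading is that a non-significant ANOVA would be reported as equivalence, but that is an inference. The mismatch does not depend on it: without a margin, no ANOVA result can confirm the prediction.

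At stake is what the pilot tells the efficacy trial about its comparator. The Aim 1 comparison is the natural place in the SAP to see whether retention, adherence and expectancy are balanced between arms, although the protocol does not itself make that link. A sizeable imbalance could be carried forward under the label of equivalence.

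**Working it through.** **Inputs from the documents.** 40 per arm (Power). Retention benchmark of 80–90% through the intervention (Aim 1), which is 32–36 per arm for measures collected only from those retained. Effect size used for sizing: within-group d = 0.40 (Power).

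**Assumptions, because the documents are silent.** Two-sided alpha 0.05 for ANOVA; two one-sided tests at 0.05 each (a 90% CI) for equivalence; the true differences and margins shown below.

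**The plan's own sample size.** No alpha or power is stated, so 40 per arm cannot be strictly reproduced. With n = ((z_α + z_power)/d)², d = 0.40 and 80% power:
- one-sided 0.05: ((1.645 + 0.842)/0.40)² = 38.6, so 39 (41 by the t distribution);
- two-sided 0.05: 49.1, so 50 (52 by the t distribution).

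The one-sided version comes close to 40. It is a within-group calculation and has no bearing on equivalence.

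**How often ANOVA misses a real difference.** With two arms, ANOVA is the two-sample t test, with noncentrality d·√(n/2) on 2n − 2 degrees of freedom. The retention rows come from exact enumeration of ANOVA on 0/1 outcomes.

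| True difference | n per arm | P(non-significant) |
|---|---|---|
| Retention 90% vs 80% | 40 | 75% |
| Retention 90% vs 75% | 40 | 56% |
| 0.4 SD | 40 | 58% |
| 0.5 SD | 40 | 40% |
| 0.5 SD | 32 | 50% |

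**Worked case: 36/40 (90%) vs 30/40 (75%) retained.**
- Between-arm mean square: 40 × 0.15²/2 = 0.45.
- Within-arm mean square: (40 × 0.90 × 0.10 + 40 × 0.75 × 0.25)/78 = 11.1/78 = 0.142.
- F = 0.45/0.142 = 3.16 on 1 and 78 degrees of freedom, p = 0.079.
- Standard error of the difference: √(0.09/40 + 0.1875/40) = 0.083.
- 90% CI: 0.15 ± 1.645 × 0.083, or 1 to 29 points.
- 95% CI, the level that matches the 5% test: −1 to 31 points.

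The ANOVA is non-significant, yet either interval allows a gap of nearly 30 points.

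**What 40 per arm can show.** The 90% CI half-width for a mean difference is t(0.95, 78) × √(2/40) = 1.665 × 0.2236 = 0.37 SD (0.42 SD at 32 per arm). For retention it is 1.645 × √(2p(1 − p)/40): 11 points at p = 0.90, 13 at 0.85 and 15 at 0.80.

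Chance of meeting an equivalence margin with 40 per arm and no true difference:

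| Margin | Chance |
|---|---|
| 0.4 SD | 11% |
| 0.5 SD | 43% |
| 0.66 SD | 80% |
| 20 points, retention 80% in both arms | 46% |
| 20 points, retention 85% in both arms | 61% |
| 20 points, retention 90% in both arms | 80% |

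**The case against.** The best case against is about weight. The study objectives state the first primary hypothesis as meeting the benchmarks; equivalence appears only in the SAP's Aim 1. Feasibility is judged mainly against the benchmarks, and no progression rule, sample size or efficacy claim rests on the ANOVAs. The plan never says that non-significance will be read as equivalence, and the word may be meant loosely as comparability. These points are fair. They confine the problem to the between-arm part of Aim 1, but Aim 1 is one of two primary aims and its prediction still has no analysis that could support it.

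The benchmarks cannot serve as margins. They are absolute targets and set no limit on a difference between arms. Nor are they stated per arm: in the worked case pooled retention is 66/80 = 82.5%, inside the 80–90% range, although one arm is at 75%. That case is therefore not a benchmark failure under the plan; it shows only that the ANOVA can miss a 15-point gap. The tertiary models under Aim 2 do not fill the gap either, because they also test for differences.

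The sizes of difference and the margins used here are illustrative, since the documents do not say what gap would matter. ANOVA could also stay as a test of difference if the wording were changed and intervals added. Neither point rescues the text as written.

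**Conclusion.** The concern holds. As written, the Aim 1 between-arm analysis cannot support the prediction of equivalence. That conclusion is a matter of logic and needs no assumed numbers.

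The size of the risk rests on the assumed alpha and the chosen true differences. On those terms, the planned test would miss a 10-point retention gap about three times in four and a half-SD gap about two times in five. Formal equivalence is within reach at this sample size only for wide margins, about 0.66 SD for 80% power.

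This should be fixed before analysis. The comparison with the feasibility benchmarks and Aim 2 stand as they are.

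**What to change.** For each post-randomisation feasibility or acceptability measure, replace the ANOVA with the between-arm difference and its 90% CI: a risk difference for retention, and a mean difference for adherence and expectancy. Make this the default report and remove the word equivalence from both the prediction and the planned analysis. Claim equivalence only for a measure whose margin is written into the SAP in advance and whose whole 90% CI lies inside that margin (two one-sided tests). State for each measure whether the denominator is everyone randomised or only those retained.

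The cost is SAP wording, plus a justified margin for any measure on which equivalence is to be claimed. No new data are needed. The downside is that several measures will probably be reported as inconclusive, which is an accurate account of what 40 per arm can show. The intervals will also be more useful than p-values in planning the efficacy trial.

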- Mindfulness training is expected to reduce daily life stress, normalize stress biology, and reduce markers of inflammation from pre-intervention to post-intervention and one-month follow-up.

Exploratory aims involve (1) developing machine learning models to estimate daily life stress from passive sensor data and (2) using these models to inform future JIT intervention.

Methods

Participants:

80 participants will be recruited. English-speaking adults (ages 18-29 years) who report moderate-to-severe physical, emotional, or sexual abuse in childhood (based on Childhood

[figure not shown]
Trauma Questionnaire thresholds) and own data-enabled Android or iOS smartphones will be recruited in Pittsburgh. Those with severe mental health diagnoses (e.g., psychosis) will be excluded for safety. The sample is expected to be 65% white, 30% black, 5% other race; 5% Hispanic; and 50% female.

Recruitment:

Participants will be recruited for a study testing smartphone stress reduction programs, primarily through The University of Pittsburgh Pitt+Me research registry has nearly 30,000 potential participants ages 18-29. Interested participants will be pre-screened online for preliminary eligibility, then invited for an in-person baseline eligibility screening and visit.

Procedures:

Data will be collected across an 8-week study period as follows:

Lab visits include blood draw and questionnaire assessments. Ecological Momentary Assessment (EMA) includes surveys delivered at four random times daily and end-of-day diary assessments. Mobile sensor data collection includes AWARE phone sensor and Fitbit data.

T1: Baseline. Participants will attend a study visit to confirm eligibility, provide informed consent, complete psychosocial assessments, and prepare for the at-home assessments and intervention. Dried blood spot (DBS) samples will be collected to assess inflammatory biomarkers. During a one-week ambulatory stress assessment, participants will provide four ecological momentary assessments (EMA) and one evening diary survey daily assessing stress and resilience; stress physiology (HR) and activity (e.g., steps, sleep) via wearable device; and smartphone sensor data.

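### The Aim 1 arm comparison of assessment and sensor adherence is neither limited to post-randomisation data nor adjusted for the T1 completion rate already recorded before assignment

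*Combined protocol and SAP*

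**What the plan says.** The Aim 1 prediction is that "mindfulness and control groups will show equivalence on these measures". The planned analysis lists the benchmarks, among them "75-90% of ambulatory assessments, and provide mobile sensor data on >75% of days", and then says "ANOVAs will test for equivalence of mindfulness vs. control groups on" the feasibility and acceptability outcomes. It names no covariate, no equivalence margin and no significance level, and does not state which weeks make up the adherence score in the arm comparison.

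The timing is given elsewhere. Under Measures, the ambulatory stress assessments are "delivered to participants' smartphones at T1, T3, and T5". The same item adds that surveys during the T2 intervention period will inform adherence. Under Procedures, T1 is a one-week assessment in which "participants will provide four ecological momentary assessments (EMA) and one evening diary survey daily". Randomisation comes afterwards: "Following baseline assessments, participants will be randomly assigned to the mindfulness intervention or coping control intervention condition". Sensor data run from T1 to T5 across the 8-week study period.

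**The concern.** Completion in the T1 week cannot depend on an arm not yet assigned. If that week is part of the outcome, it adds a component in which the expected arm difference is zero and pulls the estimate toward no difference, which is the direction Aim 1 predicts. If the week is left out of the outcome but not used at all, the analysis gives up what is likely to be a good predictor of how a participant responds to surveys later.

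The SAP's wording allows either handling. The Procedures section says the active control is meant to inform the feasibility of the RCT design for future trials, so a difference between arms in assessment adherence is worth estimating well. The point is confined to the between-arm test on two measures. It does not concern the whole-sample benchmarks or the Aim 2 models.

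**Working it through.** **Plan's own figure.** There is none for this comparison. The 80 participants (40 per condition) are tied to pilot rules of thumb and a within-group effect of d=.40 on EMA stress, not to adherence.

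**Share of the score that precedes assignment**
- Surveys per ambulatory week: (4 EMA + 1 diary) × 7 = 35, taking T3 and T5 to follow the T1 schedule.
- T1, T3 and T5 pooled: 35/105 = 33.3%.
- Adding 14 T2 evening surveys: 35/119 = 29.4%.
- Adding all T2 surveys, 14 evening + 28 around lessons + 84 around prompts (3 × 2 × 14) = 126: 35/231 = 15.2%.
- T1 excluded: 0%.
- Sensor days: 1+2+1+3+1 = 8 weeks, so 7/56 = 12.5%.

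Each percentage is the shrinkage of the raw arm difference, provided the gap is the same in every post-randomisation period counted. For example, a true 15-point gap appears as 10 points when T1, T3 and T5 are pooled, and a true 15-point gap in sensor days appears as 13.1.

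**Power for survey completion**

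Assumptions, because the documents give none of these: equal weekly SDs (set to 1), the same correlation r between any two weeks, a true gap d at both T3 and T5 and none at T1, two-sided 5%, noncentral t.
- Pooled: effect 2d/3, variance (1+2r)/3.
- T3 and T5 only: effect d, variance (1+r)/2.
- T3 and T5 adjusted for T1: effect d, variance (1+r)/2 − r².

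At r = 0.5 the variances are 0.667, 0.750 and 0.500. With d = 0.5 the standardised effects are 0.333/0.816 = 0.41, 0.5/0.866 = 0.58 and 0.5/0.707 = 0.71. The adjusted analysis carries (0.25/0.500)/(0.111/0.667) = 3.0 times the information of the pooled one, and 0.750/0.500 = 1.5 times that of T3 and T5 unadjusted.

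| d = 0.5 | Pooled | T3+T5 | T3+T5 adjusted for T1 |
|---|---|---|---|
| 40 per arm, r = 0.3 | 52% | 78% | 84% |
| 40 per arm, r = 0.5 | 44% | 72% | 88% |
| 40 per arm, r = 0.7 | 38% | 67% | 96% |
| 32 per arm, r = 0.5 | 36% | 62% | 80% |

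The last row corresponds to 80% retention, inside the plan's 75-85% follow-up benchmark.

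**Sensitivity to the size of the gap.** Pooled power for a 15-point gap, 40 per arm, r from 0.7 to 0.3:
- weekly SD 15 (a 1 SD gap): 91-98%
- SD 20: 70-86%
- SD 25: 51-68%
- SD 30 (the 0.5 SD gap of the table): 38-52%

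**Would a proper equivalence test remove the problem?** Take two one-sided 5% tests with an illustrative margin of 0.5 weekly SD, a true post-randomisation gap exactly at that margin, and 40 per arm. The pooled score declares equivalence 20-26% of the time (r from 0.7 to 0.3). T3 and T5, adjusted or not, hold about 5%.

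**The case against.** The strongest objection is that the documents never say T1 enters the arm comparison. A whole-sample benchmark percentage does not define the outcome of a between-arm test, and the ANOVA could be run by wave. This stands. A reader might infer that the plan counts T1 as outcome and therefore shrinks a true difference by a third, but the text supports only that the weeks are unspecified. One third is the largest of several possible dilutions, which run down to zero. The recommendation survives because the covariate helps even if T1 is already excluded: 72% against 88% power at r = 0.5, and 78% against 84% at r = 0.3.

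A second objection is that a reader might take a real difference to be easily missed. That depends on an SD and a correlation that the plan does not give. At a gap of 1 SD even the pooled analysis has 91-98% power, so the loss matters for moderate gaps only.

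Third, reading a missed difference as equivalence comes mainly from using a difference test with no margin. This also stands: a non-significant ANCOVA on T3 and T5 would not show equivalence either. Adding a margin would not by itself cure pooling, however, as the last calculation shows.

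Fourth, the reach is limited. Retention through the intervention, lesson completion and prompt completion all arise after assignment and are unaffected. No passage makes carrying the control forward conditional on equal assessment adherence.

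**Conclusion.** The point holds as a gap in specification and an available gain in precision. For ambulatory-assessment and sensor-day adherence, the SAP neither restricts the arm comparison to post-randomisation data nor uses T1 completion as a covariate.

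The dilution is conditional on pooling: one third for survey completion with T1, T3 and T5 weighted equally, 15-29% if T2 surveys count, 12.5% for sensor days, and none if T1 is excluded. At a gap of 0.5 weekly SD and 40 per arm, moving to the adjusted analysis raises power by 32 to 58 percentage points from the pooled score (r = 0.3 to 0.7), and by 6 to 29 points from T3 and T5 unadjusted. These figures rest on the assumed equal SDs, correlation and gap. The direction does not depend on the exact values: pooling pulls the difference toward zero, and adjustment gains more the more stable a participant's completion is from week to week. The documents do not support a claim that the plan is bound to miss a difference or to declare false equivalence.

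**What to change.** In the Aim 1 planned analysis, for these two measures only:
- Define the between-arm outcome as post-randomisation completion: T3 and T5 surveys, and T2 to T5 sensor days.
- Compare the arms by ANCOVA with the participant's own T1 completion rate on the same measure as covariate.
- Report the adjusted arm difference with its confidence interval, and state that a non-significant result will not be read as equivalence.
- Leave the whole-sample benchmark percentages unchanged.

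The cost is a sentence or two in the SAP and one degree of freedom. T1 completion is already recorded for everyone randomised. The equivalence margin needs its own decision, which this change does not replace.
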